3.1 General Design

This will be a single-blinded randomized-controlled study of GAE versus placebo in a small population with knee pain secondary to arthritis to determine safety and efficacy. After IRB approval of a written informed consent and over, approximately a 24 month duration, N=21 subjects will be recruited. Only subjects ≥ 40 years will be screened for study recruitment. Subjects will be randomized in a 2:1 ratio of GAE:Placebo and will be blinded from study treatment (see flow chart below). The placebo procedure will be a diagnostic angiogram of the knee, without embolization. Appropriate measures will be taken to ensure patients and nursing staff caring for the patient are blinded to assignment. Each patient will be told at the time of recruitment that they may be randomly assigned to sham, but if after 1 month they have not had symptom improvement, their assigned procedure would be revealed and, if they had undergone a sham procedure, they will be allowed to proceed with embolization. This second procedure should be shorter than a complete angiogram and embolization, as the detailed angiogram will not need to be repeated, and therefore both arms will have similar total radiation dose.

Clinical procedures and evaluations will consist of a preoperative screening assessment to determine if the potential study subject meets the inclusion and exclusion criteria, enrollment, surgical procedure for geniculate artery embolization, and follow-up visits at 24 hours, 2 weeks, 1, 3, 6, & 12 months. An MRI will be performed after the 1-month visit in those patients who underwent embolization to detect a change in synovial vascularity and to exclude complication.

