4.2 Anticipated Number of Research Subjects

Enrollment into the investigation will be defined as providing informed consent for study participation per IRB policies.

Twenty-one (21) subjects will be enrolled and all are anticipated to complete the study.

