We will identify extreme primary endpoint values by computing studentized residuals and then conduct sensitivity analyses by deleting these outliers from the analysis datasets. We will repeat the above statistical tests and use results of the sensitivity analyses to corroborate conclusions reached in the primary analyses.

We will address the secondary study endpoint of reduction of OA by comparing frequency of OA medical therapy between the sham group, the crossover group, and the GAE group at 12 months. We will employ a chi-squared test to test the H_0 : frequency of OA medical therapy is equal for between the sham group, the crossover group, and the GAE group versus the one-sided alternative hypothesis. A p-value of < 0.05 will be taken as evidence to suggest that the frequency of OA medical between the groups. Non-significance of the p-value for this test will be considered inconclusive evidence against the null hypothesis.

Reduction in AE will be evaluated with a multilevel logistic regression model. The outcome of adverse events will be regressed on treatment status. We will employ a compound symmetric R-side covariance structure to account for dependencies arising from observations from the same patient. The H_0 : frequency of AE is equal for between the sham group and the GAE group will be assessed versus the two-sided alternative hypothesis with a statistical test of the treatment

parameter different than 0, with a p-value of < 0.05 taken as evidence to suggest that the frequency of OA medical therapy is not equal between the groups. Non-significance of the p-value for this test will be considered inconclusive evidence against the null hypothesis.

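### The adverse-event test has no fallback for an arm without events, leaves crossover events unassigned, and states its conclusion about a different endpoint

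*Combined protocol and SAP*

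**What the plan says.** Section 3.1 states that "N=21 subjects will be recruited" and that "Subjects will be randomized in a 2:1 ratio of GAE:Placebo", which gives 14 GAE and 7 sham subjects. Section 4.2 expects no losses: "Twenty-one (21) subjects will be enrolled and all are anticipated to complete the study".

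For safety, section 8.2 says "Reduction in AE will be evaluated with a multilevel logistic regression model". It continues: "The outcome of adverse events will be regressed on treatment status", and "We will employ a compound symmetric R-side covariance structure to account for dependencies arising from observations from the same patient". The null hypothesis is that "frequency of AE is equal for between the sham group and the GAE group". It is tested two-sided through the treatment parameter at 0.05. The type of test is not named, nor is the standard error. A small p-value is then "taken as evidence to suggest that the frequency of OA medical therapy is not equal between the groups".

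Sections 3.1, 5.2 and 6.5 let sham subjects without improvement at 1 month receive GAE as Arm C. The medication endpoint in section 8.2 treats these crossovers as a third group. The AE hypothesis names only two groups, and the plan defines neither treatment status nor the period over which AEs are counted.

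**The concern.** There are three separate difficulties.

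- **Sparse data.** With 7 sham subjects, an uncommon event may well not occur in that arm at all. The maximum-likelihood log odds ratio is then infinite, and what the software prints depends on details that the plan leaves open.
- **Attribution.** A crossover subject contributes follow-up after sham and then after GAE. If events in the second period are counted under the randomised arm, events after GAE enter the sham total and the contrast shrinks.
- **Decision rule.** Read literally, a significant AE result supports a statement about medication use, which is another endpoint.

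Section 3.1 gives safety as one of the trial's two purposes, and this is the only between-group safety comparison in the plan. As written, it might return no usable answer for the events that matter most.

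**Working it through.** **Inputs.** Total 21 and ratio 2:1 (section 3.1), hence n = 14 and 7. Previous complication rates are 1/13 = 7.7% and 2/13 = 15.4% (section 9.1). Risks of 10%, 30% and 50% are assumptions. The binomial calculations use one yes/no AE outcome per subject.

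**Check of the split.** The plan states no power for the AE test. Its primary-endpoint figures do confirm 14 v 7: a one-sided two-sample t test at 0.05 gives 68.95% for WOMAC (stated 69.1%) and 51.85% for VAS (stated 51.7%).

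**Chance of an empty arm, with equal risk p in both arms.** P(sham empty) = (1−p)^7; P(GAE empty) = (1−p)^14; P(at least one empty) = 1 − [1 − (1−p)^7][1 − (1−p)^14].

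| p | Sham empty | GAE empty | At least one empty |
|---|---|---|---|
| 1/13 | 57.1% | 32.6% | 71.1% |
| 2/13 | 31.1% | 9.6% | 37.7% |
| 30% (assumed) | 8.2% | 0.7% | 8.9% |
| 50% (assumed) | 0.8% | <0.1% | 0.8% |

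**What the test returns when sham is 0/7.** A logistic fit stopped after 25 Newton steps gives a log odds ratio of about 24 to 29 with a standard error of about 112,000. The model-based Wald p is above 0.999 for any GAE count from 1 to 13.

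| GAE v sham | Fisher two-sided p | Wald p |
|---|---|---|
| 4/14 v 0/7 | 0.255 | >0.999 |
| 6/14 v 0/7 | 0.061 | >0.999 |
| 7/14 v 0/7 | 0.047 | >0.999 |
| 8/14 v 0/7 | 0.018 | >0.999 |
| 10/14 v 0/7 | 0.004 | >0.999 |

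**Does repeated measurement rescue it?** No. A marginal logistic model with exchangeable correlation and 6 assumed visits per subject, fitted to 8/14 v 0/7, gives p > 0.999 with model-based standard errors. With robust standard errors p is effectively 0, and it is still effectively 0 for 1/14 v 0/7, where Fisher's p is 1.0. One unstated option therefore moves the answer from one extreme to the other.

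**How often an exact test would do better.** With sham empty, Fisher rejects only from 7/14 upward. At 10% risk in both arms, the chance of 0/7 together with at least 7/14 is 0.009%. Fisher's power for 14 v 7, by enumeration of all tables, is 0.3% at 15.4% v 7.7%, 4.6% at an assumed 30% v 10%, and 44.6% at an assumed 50% v 5%. In the last case the Wald test has 2.4%, counting empty-arm tables as non-significant.

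**Crossover.** Assume that 4 of 7 sham subjects cross over, with AE risk 10% after sham and 30% after GAE. A crossover subject's risk of any AE is 1 − 0.9 × 0.7 = 0.37. Counted by randomised arm, sham risk is (3 × 0.10 + 4 × 0.37)/7 = 25.4%. The difference from GAE is then 30 − 25.4 = 4.6 points, against 20 points by procedure.

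**The case against.** Three stronger readings are tempting, and the documents do not support them.

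- **That the plan prescribes a Wald test for AEs.** Section 8.2 names Wald only for WOMAC and VAS. It is a fair inference for a single parameter in a model with R-side covariance, but it is not written. A likelihood-ratio test in a simple per-subject logistic model gives p = 0.003 for 8/14 v 0/7, so the failure belongs to the Wald form and not to logistic regression as such.
- **That crossover AEs will be pooled into sham.** Nothing says so. Section 5.5 labels datasets A, B or C, and the medication analysis separates crossovers, so a consistent reading could keep them apart. The 4.6-point figure is one permitted outcome under assumed rates.
- **That 71% or 38% is the chance of missing a real excess.** It is only the chance of an empty arm. Most such tables would also be non-significant under Fisher's test.

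The rates themselves can be challenged. Section 9.4 records every adverse effect, serious or not. Sham subjects also undergo arterial access, and section 9.1 lists access-site discomfort as possible. The 1/13 and 2/13 figures are complications. If minor AEs are common, an empty arm for any AE is unlikely. This stands, and it limits the sparse-data problem to uncommon events.

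Safety does not rest on this test alone. There is a stopping rule for major complications (section 9.7), review by a study monitor (section 9.8.1), and a non-significant result is to be called inconclusive. These soften the consequence. They do not define the comparison, and section 8.2 gives no analysis of the primary safety endpoint in section 3.4.

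**Conclusion.** The concern holds in a limited form. The error in the decision sentence is certain and needs no assumption. The undefined treatment status and counting window are also plain from the text; dilution is a possible result, and its size depends on assumed crossover and risk figures.

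The sparse-data gap is real but conditional. It bites if an arm is empty and the unnamed test is Wald-type with model-based standard errors. An empty arm is likely (38% to 71%) only if per-subject risk is near the quoted complication rates, and is uncommon (9% or less) at 30% risk or above. An exact method gives a defined result for every table, but it does not cure the low power of 14 v 7. The change should be made, mainly so that serious AEs and major complications are reported in an interpretable way.

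**What to change.** In section 8.2:

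1. Replace the multilevel model with a per-subject analysis of two outcomes, any AE and any major complication, using a two-sided exact test (Fisher or exact unconditional).
2. Make the exact confidence intervals the main result, because power is low. For scale, the exact two-sided 95% upper limit is 41% for 0/7 (1 − 0.025^(1/7)) and 23% for 0/14 (1 − 0.025^(1/14)).
3. Compare GAE with sham over the same follow-up window in both arms, ending before any crossover, for example at the 1-month visit.
4. Report a separate exact rate for all subjects exposed to GAE, including crossovers, counted from their GAE procedure.
5. Correct the decision sentence so that it refers to AEs.

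The cost is SAP wording only; no extra data or subjects are needed. The downside is that several AEs in one subject collapse to a single indicator, so repeat events have to be listed descriptively. AEs after the common window would be described and not formally compared with sham.

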6.5 Visit 5a and 5b - 1 Month Follow-Up

Subjects will be seen in clinic or contacted by phone or by teleconference, per the subject's preference, 30 +/- 7 days following GAE or sham procedure. The WOMAC questionnaire and VAS pain score will be completed and subjects will be evaluated for possible adverse events. An MRI of the treated knee will be acquired for those subjects who underwent GAE*. Subjects will also provide an update about the necessity/frequency of pre-established conservative therapies.

For those subjects who do not report improvement in symptoms or worsening, and are in the placebo arm, they will be unblinded and offered to undergo the geniculate artery embolization (Arm C) and then followed at similar follow-up intervals to 12 months (24 hours, 2 weeks, 1 month, 3 months, 6 months, and 12 months).

*MRI is only scheduled at one month in order to evaluate for non-target ischemic injury. These types of injuries will become apparent as early as 24 hours after embolization. Infarcted tissue will still be detectable at one month. Based on our experience with embolization in other areas, it is thought extremely unlikely that new ischemic injury related to the procedure will develop after the one-month follow-up. Additionally, findings that would be detected on later scans may be unrelated to the procedure and confound the data.

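### The adverse-event test regresses repeated observations on treatment alone; if risk is higher early, crossover out of sham after month 1 can make equal risk look like fewer events with GAE

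*Combined protocol and SAP*

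**What the plan says.** Section 8.2 (Statistical Methods) states: "Reduction in AE will be evaluated with a multilevel logistic regression model". The only regressor named is treatment: "The outcome of adverse events will be regressed on treatment status". A compound symmetric structure is added to "account for dependencies arising from observations from the same patient", so the data are repeated observations per subject. The null hypothesis is that the "frequency of AE is equal for between the sham group and the GAE group"; it "will be assessed versus the two-sided alternative hypothesis with a statistical test of the treatment" parameter, "with a p-value of < 0.05 taken as evidence". By contrast, the WOMAC and VAS models in the same section include time.

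Section 3.1 (General Design) sets "follow-up visits at 24 hours, 2 weeks, 1, 3, 6, & 12 months", and section 9.4 has subjects asked about adverse effects at each one. Section 6.5 says of sham subjects without improvement at month 1: "they will be unblinded and offered to undergo the geniculate artery embolization (Arm C"), after which a new 12-month schedule starts. GAE subjects have no such exit.

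The AE hypothesis names two groups, whereas the medication test in 8.2 also names a crossover group. The plan does not say whether Arm C observations are dropped, kept as sham or counted as GAE. It also does not define the unit of observation or the at-risk window.

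**The concern.** Two features combine. First, the arms can differ in their mix of contacts: every GAE subject contributes three contacts up to month 1 and three later, while a sham subject who crosses over contributes only the first three as sham. Second, the protocol expects procedural events to come early. Section 6.3 places most complications within the day-1 visit window, and section 6.5 considers new procedure-related ischemic injury after month 1 very unlikely. A model with treatment alone compares average risk per contact. It would then average sham over mostly high-risk contacts and GAE over all six.

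At stake is the only between-arm AE test that the plan specifies. A difference could be reported as a reduction in AEs when it reflects who crossed over.

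**Working it through.** **The plan's own figures.** None is given for the AE comparison. The only computed figures are the powers in section 8.1 (69.1% and 51.7%). A one-sided 5% two-sample t-test with 14 v 7 subjects gives 68.95% and 51.85%. This supports a 14:7 split but says nothing about the AE model.

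**Inputs from the documents.** N = 21 at 2:1 gives 14 GAE and 7 sham. There are six contacts, three of them up to month 1. Crossover is open to sham only, after month 1.

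**Inputs assumed.** The same risk per contact holds in both arms, with two front-loaded profiles: A = 30/20/15/5/5/5% and B = 15/8/5/3/3/3%. The number of sham subjects crossing over is k = 3, 5 or 7 of 7, censored at crossover.

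**Formulas.** Let E be the summed risk over the first three contacts and L over the last three.
- GAE average = (E + L)/6
- Sham average = [7E + (7 − k)L] / [21 + 3(7 − k)]
- Odds ratio (OR) = GAE odds / sham odds

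Profile A: E = 0.65, L = 0.15, GAE = 0.80/6 = 13.3% (odds 0.154). Profile B: E = 0.28, L = 0.09, GAE = 0.37/6 = 6.2% (odds 0.0657).

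| k | Sham, A | OR, A | Sham, B | OR, B |
|---|---|---|---|---|
| 3 | 5.15/33 = 15.6% | 0.83 | 2.32/33 = 7.0% | 0.87 |
| 5 | 4.85/27 = 18.0% | 0.70 | 2.14/27 = 7.9% | 0.76 |
| 7 | 4.55/21 = 21.7% | 0.56 | 1.96/21 = 9.3% | 0.64 |

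With k = 0, or with the same risk at every contact, both averages agree and the OR is 1.00.

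**Other ways to treat Arm C (profile A, k = 5).**
- Counted as GAE: 19 × 0.80 / (19 × 6) = 13.3%, so the OR stays at 0.70.
- Kept as sham: (4.85 + 5 × 0.80)/(27 + 30) = 8.85/57 = 15.5%, OR 0.84.

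**False-positive rate.** Null trials of 14 v 7 were simulated with a marginal logistic model, exchangeable correlation and a Wald test at two-sided 5%, sham being censored at crossover. The settings documented in detail use a subject effect with SD 0.7 on the logit scale.
- Profile A, k = 3 to 7: about 9% to 17%, nearly all favouring GAE. Separate runs of 400 to 600 trials gave 8% at k = 3, 12% to 15% at k = 5, and 5.5% to 6.5% with no crossover.
- Profile B: about 6% to 10%. One set of runs that kept every trial in the denominator gave 4% at k = 3, 5.5% at k = 5 and 1.5% with no crossover.
- Flat 10% per contact, k = 5: 5.5%.
- Test limited to the period up to month 1: about 2% to 7%.

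**Effect of a time term.** A further set of simulations used first-three-contact risks from 20/15/10% to 40/20/10%, later risks of 3% to 5%, a subject SD of 0.5 and 75% to 100% crossover. Rejection was 10% to 27% without a time term and 4% to 8% with a coarse period term. Fits that did not converge were dropped.

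**The case against.** The strongest objection is that the size comes from assumptions. Section 9.1 cites complication rates of 1/13 and 2/13 from earlier series, well below profile A's early risks. At lower rates the test stays near its nominal level. This stands as a limit on size. However, those figures count complications and not all AEs, section 9.1 lists discomfort as possible, and even at lower rates rejection rises with crossover and favours GAE.

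It can also be said that the more basic gap is the undefined unit, window and Arm C assignment, and that a time term matters only once these are set. That is fair, and the fix covers all three.

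A reader might infer three stronger things, none of which the documents support.
- *The bias arises however risk behaves and however Arm C is handled.* It needs risk that varies between contacts; flat risk gives none. Keeping crossover contacts as sham weakens it, and those subjects have in fact had two procedures.
- *The bias could reverse strongly against GAE through longer exposure.* That belongs to an analysis of any AE per subject. Section 8.2 describes repeated observations per subject.
- *The trial's safety conclusion is compromised.* The primary safety endpoint (3.4) and the stopping rule (9.7) concern major complications and do not use this test. All AEs are also summarised (9.8.1), and 8.2 treats non-significance as inconclusive.

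**Conclusion.** The concern holds in conditional form. As written, the AE model can turn equal risk into an apparent advantage for GAE if two conditions are met: some sham subjects cross over, and AE risk per contact is higher early. The design provides for the first, and sections 6.3 and 6.5 support the second for procedural events.

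Under profile A with 3 to 7 of 7 sham subjects censored at crossover, the spurious odds ratio is about 0.83 to 0.56; with 5 of 7 kept as sham it is about 0.84. Across profiles A and B the nominal 5% test rejects in roughly 6% to 17% of null trials, the low end being close to nominal. These are illustrations under assumed rates and crossover, not predictions. With 21 subjects the AE test is imprecise in any case. It is not a listed endpoint, so the consequence is confined to this between-arm AE comparison. The change is worth making because it is cheap.

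**What to change.** State in section 8.2:

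*The sham–GAE comparison of AEs uses the randomised arms and events from the first procedure up to the month-1 visit, before any Arm C procedure. Findings detected only by the month-1 MRI are excluded from this test and reported separately. Later events and Arm C events are described by procedure received and length of follow-up.*

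The same paragraph should define the unit of observation.

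The MRI exclusion is needed because section 6.5 schedules that scan only after GAE, and section 9.4 allows abnormal test findings to count as adverse effects. Without it, ascertainment would differ between arms inside the window.

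If all contacts are modelled instead, stop sham observation at crossover and add a two-level period term (up to month 1 v later). A six-level visit factor is too fragile: under profile A with 5 of 7 crossing over, 74% of simulated trials had at least one visit with no events, so that visit's coefficient could not be estimated. The period term is second best. Crossover depends on lack of improvement, which may itself be related to AEs such as pain, so the term may not remove all bias, and some fits may fail with sparse events.

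The cost is a wording change and no new data. The downside is small: late events leave the formal test and are only described.

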6.11 Visit 9c-1 month follow-up for unblinded subjects

Subjects will be seen in clinic 30 +/- 7 days following GAE. The WOMAC questionnaire and VAS pain score will be completed and subjects will be evaluated for possible adverse events. An MRI of the treated knee will be acquired. Subjects will also provide an update about the necessity/frequency of pre-established conservative therapies.

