9.4 Recording of Adverse Events

Research subjects will be questioned about adverse effects in person or by telephone the day following the procedure. In addition, they will be given a pager number to reach a physician on call, 24 hours a day, to report adverse effects and receive medical advice. The subjects will also be questioned about possible adverse effects at each follow-up visit.

All observed or volunteered adverse effects (serious or non-serious) and abnormal test findings, regardless of treatment group, if applicable, or suspected causal relationship to the investigational device or, if applicable, other study treatment or diagnostic product(s) will be recorded in the subjects' case histories. For all adverse effects, sufficient information will be pursued and/or obtained so as to permit 1) an adequate determination of the outcome of the effect (i.e., whether the effect should be classified as a *serious adverse effect*) and; 2) an assessment of the causal relationship between the adverse effect and the investigational device or, if applicable, the other study treatment or diagnostic product(s).

Adverse effects or abnormal test findings felt to be associated with the investigational device or, if applicable, other study treatment or diagnostic product(s) will be followed until the effect (or its sequelae) or the abnormal test finding resolves or stabilizes at a level acceptable to the investigator-sponsor.

An abnormal test finding will be classified as an *adverse effect* if one or more of the following criteria are met:

- The test finding is accompanied by clinical symptoms
- The test finding necessitates additional diagnostic evaluation(s) or medical/surgical intervention; including significant additional concomitant drug treatment or other therapy
 - Note: simply repeating a test finding, in the absence of any of the other listed criteria, does not constitute an adverse effect.
- The test finding leads to a change in study protocol or discontinuation of subject participation in the clinical research study
- The test finding is considered an adverse effect by the Sponsor-Investigator.

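### Incidental findings on a scheduled 1-month MRI that only embolized subjects have can count as AEs, so the sham-versus-GAE AE odds ratio leans against GAE by an amount the documents do not fix

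*Combined protocol and SAP*

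**What the plan says.** **Analysis.** Section 8.2 plans a multilevel logistic model: "The outcome of adverse events will be regressed on treatment status". The null hypothesis is that the "frequency of AE is equal for between the sham group and the GAE group", tested two-sided at 0.05. No event type or source of detection is excluded, flagged or analysed separately.

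**Imaging.** Section 6.5, on the 1-month visit, states: "An MRI of the treated knee will be acquired for those subjects who underwent GAE". Section 3.1 agrees: "An MRI will be performed after the 1-month visit in those patients who underwent embolization". The stated reason is safety: "MRI is only scheduled at one month in order to evaluate for non-target ischemic injury". For blinded subjects, sections 6.3, 6.6 and 6.8 allow other follow-up MRI only as part of the work-up of a suspected AE, and section 7.1 says the same of symptoms reported at any time. Sham subjects who cross over are scanned one month after their embolization (section 6.11: "An MRI of the treated knee will be acquired").

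**AE definition.** Section 9.4 lists four criteria, any one of which makes an abnormal test finding an adverse effect. One requires symptoms. The others do not, among them "The test finding necessitates additional diagnostic evaluation(s) or medical/surgical intervention" and the sponsor-investigator's own judgement.

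**The concern.** Taken together, these sections make the chance of detecting an AE depend on the arm. Every subject has symptomatic knee OA, so an incidental structural finding is plausible in either arm, but after the procedure it is looked for routinely in only one. Randomization does not remove a difference in detection that arises after allocation.

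Section 6.5 recognises the hazard, since it warns that unrelated findings on later scans could confound the data. It does not apply that reasoning to the 1-month scan, which is the scan given to one arm only.

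Safety is part of the trial's stated purpose (section 3.1). If the arms had the same true risk, the planned comparison would still be expected to show more AEs on GAE whenever any MRI-only finding met a 9.4 criterion. The model as specified cannot separate that excess from a true one.

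**Working it through.** **Figures in the plan.** The documents state no AE rate, no MRI finding rate and no power for the AE test, so there is no AE figure to reproduce. The arm sizes follow from 21 subjects at 2:1: 14 GAE and 7 sham. The section 8.1 power figures confirm this split. With a one-sided t-test at 0.05, WOMAC has d = 0.16 × 12.2 / 1.9 = 1.027 and power 68.95% (stated 69.1%). VAS has d = 0.15 × 72 / 13.3 = 0.812 and power 51.85% (stated 51.7%). Neither figure bears on the AE question.

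**Assumptions (none from the documents).** Let p be the risk per subject of an AE detected by means common to both arms, equal in the two arms. Let q be the share of otherwise event-free GAE subjects in whom the scheduled MRI alone produces an AE. Sham subjects are given no MRI-only events.

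**Formulas.**
- Observed GAE risk: P = p + (1 − p)q
- Extra GAE subjects with an AE: 14 × (1 − p)q
- Spurious odds ratio (true value 1): P / [p(1 − q)]

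**Results at p = 20%.**

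| q | Observed GAE risk | Extra of 14 | Odds ratio |
|---|---|---|---|
| 2% | 0.216 | 14 × 0.8 × 0.02 = 0.22 | 0.216 / 0.196 = 1.10 |
| 5% | 0.24 | 14 × 0.8 × 0.05 = 0.56 | 0.24 / 0.19 = 1.26 |
| 10% | 0.28 | 14 × 0.8 × 0.10 = 1.12 | 0.28 / 0.18 = 1.56 |
| 20% | 0.36 | 14 × 0.8 × 0.20 = 2.24 | 0.36 / 0.16 = 2.25 |
| 30% | 0.44 | 14 × 0.8 × 0.30 = 3.36 | 0.44 / 0.14 = 3.14 |

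**Sensitivity to p, for q from 10% to 30%.** The odds ratio runs from 2.11 to 5.29 at p = 10%, from 1.37 to 2.43 at p = 30%, and from 0.46 / 0.36 = 1.28 to 0.58 / 0.28 = 2.07 at p = 40%.

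**Effect on the test.** Subjects with at least one AE were compared, 14 against 7, by exact binomial enumeration at two-sided 0.05. This is a subject-level stand-in for the planned multilevel model. At p = 20%, Pearson chi-squared rejects in 6.0% of trials with q = 0, then 5.6%, 9.9% and 17.6% at q = 10%, 20% and 30%. Fisher's test rejects in 1.5%, then 1.9%, 4.7% and 10.3%. At q = 10% the estimate is already distorted while the rejection rate has barely moved.

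**The case against.** **The rates are assumed, and the nearest evidence points low.** Section 1.2 reports that MRI follow-up in the cited 72-patient GAE cohort showed neither osteonecrosis nor progression of degenerative change. This does not cover every possible finding, and the number scanned is not given. It is still a reason to extend the range toward zero, as the 2% and 5% rows do.

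**A reader might infer that every MRI abnormality becomes an AE.** It does not, because a finding must meet a section 9.4 criterion. Section 6.1 also provides a baseline MRI that could identify old changes. However, no comparison rule is written, and an earlier clinical scan may serve as baseline.

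**A reader might infer that sham subjects have no route to such detection.** That is too strong. A symptom-prompted scan can show an incidental finding, and crossover subjects have the scheduled scan after embolization. Section 8.2 does not say which group their later events join. Counting them as sham would narrow the detection gap but would put embolization events into the comparator.

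**Other safeguards exist.** Section 9.5 assesses causality event by event, and section 9.8.1 summarizes all AEs. Both help a careful reader, but the 8.2 test does not use causality.

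**The consequence is limited.** The primary safety endpoint (section 3.4) and the stopping rule (section 9.7) concern major complications and do not use this test. The comparison is not a listed endpoint, and section 8.2 treats non-significance as inconclusive.

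**Dropping all MRI-only events would create the opposite bias.** The scan exists to find non-target ischemic injury, a true harm of GAE. A comparison that omitted silent injury would flatter GAE. This objection stands in full and shapes the fix.

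**Conclusion.** The point holds as a problem of unequal ascertainment. The direction follows from the text: whenever an incidental MRI-only finding qualifies under section 9.4, the sham-versus-GAE odds ratio moves against GAE. The size cannot be taken from the documents. At an assumed 20% common risk it is about 0.2-0.6 extra GAE subjects of 14 for an MRI-only AE rate of 2-5%, and about 1.1-3.4 (odds ratio 1.56-3.14) for 10-30%. These figures assume equal true risk and no MRI-only detection in sham.

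Two stronger readings are not supported. One is that the test is bound to give false significant results: at a 10% MRI-only rate the rejection rate hardly changes, and a material rise needs about 20% or more. The other is that all MRI-detected events are artefact, since ischemic injury from embolization belongs in the safety record. The main harm is an AE estimate in which true and detection-driven excess are mixed.

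**What to change.** 1. Add a CRF field for how each AE was first detected: spontaneous report, elicited at a scheduled contact, symptom-prompted work-up, or scheduled 1-month MRI only.
2. In section 8.2, report the sham-GAE comparison twice: for all AEs, and for AEs ascertained the same way in both arms (reported or elicited at scheduled contacts, or found on symptom-prompted work-up), before any crossover embolization. Base any between-arm conclusion on both results.
3. Report MRI-only findings in full and descriptively for embolized subjects (GAE arm and Arm C) against baseline MRI, with ischemic injury listed separately.

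The cost is one CRF field and one extra analysis, with fewer events in the common-ascertainment comparison. Stopping at crossover also shortens sham follow-up, so follow-up time should be shown by arm, or the common-ascertainment result also given up to the 1-month visit. The imaging schedule and the stopping rule are unchanged, and no safety data are lost.
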